2.2 DOSE RATIONALE

In this study, our primary purpose is to investigate how changes in blood glucose level affect neuronal excitability. We will administer a 75g load of glucose (oral glucose tolerance test, OGTT) that complies with the standard guidelines for diagnosing diabetes

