2.3.2 RESEARCH HYPOTHESES

We hypothesize that glucose administration modulates neuronal excitability measured by TMS-induced MEPs and TEPs. We also hypothesize that frontal theta (4-8Hz) and left frontal alpha (8-12Hz) oscillations, which represent an engaged (theta) and disengaged (alpha) cortical state, are modulated in response to glucose administration compared to water drink. The modulation of neuronal excitability and brain network dynamics is depending on blood glucose level

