8.2.1 PHYSICAL

Risk of Injury and Discomfort: Non-invasive brain stimulation has been used without any reports of serious side-effects for more than a decade and TMS has been cleared for use in the USA by the FDA. The stimulation made nothing to do with electroconvulsive therapy that applies many orders of magnitude higher stimulation current. Some participants report a scalp pain, tingling, burning, or itching on the stimulation site but no other side effects have been noted. In order to monitor these side-effects, we will be administering side effects stimulation questionnaire after each stimulation session to determine whether these effects were experienced. Research personnel present during these sessions will also check in with the participant periodically during the stimulation to see whether they are comfortable. If any side-effect occurs (rated by the participant as stronger than “moderate”) or the participant is experiencing severe discomfort, the stimulation will be immediately stopped.

Risk of Bleeding: The glucose tolerance test is a medical test in which glucose is given and blood samples taken afterward to determine how quickly it is cleared from the blood. The test is usually used to test for diabetes, insulin resistance, impaired beta cell function, and sometimes reactive hypoglycemia and acromegaly, or rarer disorders of carbohydrate metabolism. We strictly follow the medical guidelines using an FDA-cleared device and sampler and blood sampling will be immediately stopped if any unexpected bleeding occurs.

Risk of Glucose Ingestion: The risks associated with glucose ingestion in healthy participants are minimal.

The potential side effects include nausea, sweating, light-headedness, vomiting, bloating, headache, diarrhea, and constipation. Serious side effects from the test are very uncommon.

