11.1 STATISTICAL ANALYSIS STRATEGIES

Outcome variables include:

Aim 1

- 1) motor-evoked potentials to measure corticospinal excitability (unit: uV)
- 2) TMS-evoked potentials to measure cortical excitability (unit: uV)

Aim 2

- 1) EEG spectral power in the theta-band (4-8Hz) averaged over frontal EEG channels to measure engaged brain network dynamics (unit: dB).
- 2) EEG spectral power in the alpha-band (8-12Hz) averaged over left frontal EEG channels to measure disengaged brain network dynamics (unit: dB).

For all analyses, outcome measures are analyzed as the difference from baseline metrics before the GTT. The repeated measures of primary outcome will be fitted into general linear mixed effect model where baseline measures (continuous), time of measures (categorical), treatment method (binary) and time by treatment as fixed effects, while the within-subject effect among different time point (0, 30, 60, 120, 180 minutes) is modeled as random intercept assuming autoregression model (AR(1)) as covariance structure. The two sided Wald-test of treatment method (fixed effect) between the verum GTT versus control GTT condition is our primary result of interest. We hypothesize a significant main effect for factor GTT but no effect for factor time nor the interaction of GTT by time. We hypothesize that verum-GTT will modulate corticospinal and cortical excitability. In case we do find a significant interaction of GTT by time, we will use post-hoc contrast test to compare the overall differences between verum-GTT versus control-GTT at each time point and correct for multiple comparisons using false discovery rate (FDR) method. All hypothesis tests that are observed to be not statistically significant will be reported as being inconclusive. Based on the nature of our study design, we assume missing data to be minimal, where linear mixed effect model is robust to handle such missing value situations without creating any obvious bias. For all the result tables of statistical analysis, statistical estimates of population parameters will be tabulated along with corresponding confidence intervals (CIs). Given the lack of any comparable study in the literature, we performed a power analysis guided by the number of participants we are able to enroll based on the size of the grant. Briefly, with a sample of N=20 participants, we will be able to detect an effect size of $d_z = 0.66$ with $\alpha = 0.05$ and $\beta = 0.2$. Power analysis was performed with G*Power.

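### Does the primary treatment test need a written contrast, and should the 0-minute measure be left out of it?

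*Combined protocol and SAP*

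**What the plan says.** Section 11.1 analyses each outcome as a change from the pre-drink baseline. The mixed model has baseline, time (categorical), treatment (binary) and time by treatment as fixed effects, over 0, 30, 60, 120 and 180 minutes. The primary result is defined thus: "The two sided Wald-test of treatment method (fixed effect) between the verum GTT versus control GTT condition is our primary result of interest". The expected pattern follows: "We hypothesize a significant main effect for factor GTT but no effect for factor time nor the interaction of GTT by time". Per-time comparisons are conditional: "In case we do find a significant interaction of GTT by time, we will use post-hoc contrast test", with false discovery rate correction. Estimates are to be tabulated with confidence intervals, and non-significant tests are to be reported as inconclusive.

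Elsewhere the protocol ties the effect to glucose itself. Section 2.2 says "our primary purpose is to investigate how changes in blood glucose level affect neuronal excitability", and section 2.3.2 says "The modulation of neuronal excitability and brain network dynamics is depending on blood glucose level". The physical-risk part of section 8.2 describes the tolerance test as one in which "glucose is given and blood samples taken afterward to determine how quickly it is cleared from the blood". Sections 4 and 5.2 place the 0-minute measure after the drink and separate from baseline, so it is one of the five modelled outcomes.

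**The concern.** Three features look wrong together.

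- **Coding.** With an interaction in the model, the meaning of the treatment coefficient depends on how time is coded. With 0 minutes as the reference level, it is the 0-minute difference only. Two analysts could then report different primary results from the same data.
- **Dilution.** Read as a main effect, the test averages in a measure taken just after the drink, when blood glucose may hardly have moved. That would understate the later effect and cost power in a trial whose size is fixed at 20 by funding.
- **Flat expectation.** Expecting no interaction sits awkwardly beside a hypothesis that the effect depends on glucose level, since glucose should change over three hours. The per-time tests run only if an interaction test succeeds, and the power of that test depends on a correlation the plan does not state.

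**Working it through.** **Inputs.** N = 20 in a crossover, dz = 0.66, alpha = 0.05 two-sided, beta = 0.2, five post-drink times (sections 4, 4.1 and 11.1). Assumed, because the documents are silent: the correlation r between times of the glucose-minus-water differences (AR(1) with equal steps, or compound symmetry, CS), equal variances, and the effect profile. The baseline covariate is ignored.

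**The plan's own figure.** For a paired t-test with 19 df and noncentrality 0.66 × √20 = 2.95, power is 79.9%. The stated dz reproduces.

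**Coding.** Let s5 and s4 be the SDs of the mean over all five times and over 30 to 180 minutes, with each single-time SD equal to 1. If a constant effect gives dz 0.66 on the five-time mean, the 0-minute difference alone has dz = 0.66 × s5:

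- r = 0: 0.66 × 0.447 = 0.295, power 24%
- r = 0.5, AR(1): 0.66 × 0.667 = 0.440, power 46%
- r = 0.5, CS: 0.66 × 0.775 = 0.511, power 58%
- no effect at 0 minutes: 5%

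In one simulated data set with true effects 0, 1, 1, 1, 1, the reference-coded coefficient was −0.08 (p = 0.61) and the averaged difference was 0.84 (p < 0.001). The two readings are therefore far apart, and it matters which one the text supports.

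**Which reading the text supports.** Section 11.1 names a main effect for the drink factor, lists time and the interaction as separate items, and keeps comparisons at single times for a later post-hoc step. In that factorial language a main effect averages over the levels of time. A test at 0 minutes alone would be one of the post-hoc contrasts, not the primary test.

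**Keep or drop 0 minutes.**

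- No effect at 0 minutes, equal effect later, dz 0.66 on the 30 to 180 minute mean: the five-time mean carries 4/5 = 0.80 of the effect, so dz5 = 0.66 × 0.80 × s4/s5.
- Constant effect, dz 0.66 on the five-time mean: dropping 0 minutes gives dz4 = 0.66 × s5/s4.
- Break-even share f of the later effect present at 0 minutes: (4 + f)/(5 × s5) = 1/s4, so f = 5 × s5/s4 − 4. Below f the later mean has more power; above it the five-time mean does.

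| r | s5 | s4 | No effect at 0 min: five-time power (later mean 79.9%) | Constant effect: later-mean power (five-time 79.9%) | f |
|---|---|---|---|---|---|
| 0 | 0.447 | 0.500 | 70.7% | 70.7% | 0.472 |
| 0.5, AR(1) | 0.667 | 0.718 | 67.4% | 73.9% | 0.645 |
| 0.5, CS | 0.775 | 0.791 | 62.8% | 78.3% | 0.899 |
| 0.9, AR(1) | 0.923 | 0.939 | 62.5% | 78.6% | 0.915 |
| 0.9, CS | 0.959 | 0.962 | 61.3% | 79.7% | 0.986 |

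For example, at r = 0, dz5 = 0.66 × 0.80 × 0.500/0.447 = 0.590 and dz4 = 0.66 × 0.447/0.500 = 0.590, so the gain in one case equals the loss in the other.

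**If the effect fades as glucose is cleared.** Take an illustrative profile 0, 1, 1, 0.5, 0 with dz 0.66 on the 30 to 60 minute mean. At r = 0.5 the 30 to 180 minute mean has 56% (AR(1)) or 48% (CS) power, against 44% or 35% for the five-time mean. The alternative contrast is better here but is itself diluted, so it does not cure the problem it is meant to address.

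**Interaction gate.** No effect at 0 minutes, with the later effect sized for 80% power had it been present at all five times; F test on 4 and 76 df, covariance taken as known:

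| r | 0 | 0.3 | 0.5 | 0.7 | 0.9 |
|---|---|---|---|---|---|
| AR(1) | 12.5% | 20% | 33% | 66% | 99.9% |
| CS | 12.5% | 33% | 60% | 92% | about 100% |

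The gate is weakest at r = 0, where dilution is mildest (70.7%). Dilution is worst at r = 0.9 (61% to 63%), where the gate almost always opens. The two worst cases do not coincide.

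**The case for a change.** The strongest argument for acting is that the sentence defining the primary test speaks of a fixed effect, not a main effect. Default software output under reference coding would print a coefficient that answers a different question, and one line of text would remove the doubt without any biological assumption. It is true that no weights are written and that the two readings can give opposite results. But the sentence on the expected pattern resolves the meaning, and a statistician fitting an interaction model would request the averaged contrast. The 24% to 58% and 5% figures describe a reading the text disfavours.

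The second argument is that a level-dependent effect should vary over three hours, so the flat expectation weakens the primary test. The tension is real but mild. A threshold or lasting effect could be flat, and the dependence in section 2.3.2 could hold between people. The section 8.2 sentence is general risk text about the procedure. A small effect at 0 minutes is plausible, but it is an inference: the documents give no glucose curve and do not define when 0 minutes starts.

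The third argument is that per-time tests should not wait for the interaction test. That is a reporting preference. It would add 5 × 4 = 20 adjusted tests across the four outcomes, in a plan that already tabulates estimates with intervals.

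**Conclusion.** No change follows. The missing weights are a gap that the plan's own main-effect wording fills: the primary quantity is the equal-weight mean glucose-minus-water difference over the five post-drink times. Including 0 minutes is a fair trade-off. It lowers power to 61% to 71%, against 80% for the 30 to 180 minute mean, if there is no effect at 0 minutes and an equal effect later. It protects against a fall from 80% to between 71% and 80% if the effect is constant, as the plan expects. The break-even share runs from 47% to 99% of the later effect, depending on a correlation nobody has stated, so the documents cannot show that the team chose wrongly. The no-interaction expectation is in mild tension with section 2.3.2 but does not contradict it, and a glucose-weighted time contrast would not test dependence on measured glucose anyway.

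The remaining risk is limited in a funding-sized pilot meant to inform a later study (section 11.2), with intervals tabulated, corrected contrasts planned after an interaction, and non-significance reported as inconclusive. All power figures except the reproduced 79.9% rest on the assumed profiles and correlations shown.

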11.2 CHOICE OF SAMPLE SIZE

The choice of sample size was based on expert opinion and funding limit; we conjecture that 20 participants may be sufficient to provide adequate precision for the estimators of variance components and other parameters for which information is needed to plan a future study. As a rough and indirect assessment of the precision afforded by studying a sample of 20 subjects, we considered that an estimate of the proportion of subjects in the target population that would experience a greater decrease in MEP and TEP amplitude with verum-GTT (Glucose), relative to control-GTT(water) for an observed estimate of 50%, the 95% confidence interval would span [50% ± 20%]. Or, if 80% was the observed estimate, then the 95% CI would span [80% ± 16%].

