3 SUBJECT SELECTION AND WITHDRAWAL

A total of 20 healthy participants will be recruited for this study and all data will be collected at UNC-CH. No specific plans have been made to enroll participants from vulnerable populations.

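### The two illustrative 95% confidence intervals in section 11.2 (±20% and ±16%) are narrower than 20 subjects give under the symmetric formula (±21.9% and ±17.5%)

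*Combined protocol and SAP*

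**What the plan says.** Section 11.2 opens with the basis for the number of participants: "The choice of sample size was based on expert opinion and funding limit". It then offers a numerical illustration, introduced as follows: "As a rough and indirect assessment of the precision afforded by studying a sample of 20 subjects". The quantity is "an estimate of the proportion of subjects in the target population that would experience a greater decrease in MEP and TEP amplitude" on glucose relative to water. Two cases are given. In the first, "for an observed estimate of 50%, the 95% confidence interval would span [50% ± 20" percentage points; in the second, "if 80% was the observed estimate, then the 95% CI would span [80% ± 16" percentage points. No interval method is named.

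The number 20 is consistent elsewhere. Section 3 states: "A total of 20 healthy participants will be recruited for this study". Section 4.1 assigns ten participants to each of two sequences. The power statement in section 11.1 also rests on 20: "with a sample of N=20 participants, we will be able to detect an effect size of" dz = 0.66.

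**The concern.** A confidence interval for a proportion is fixed by the observed proportion, the number of subjects, the confidence level and the method. The section gives the first three, and its plus-or-minus notation points to the symmetric normal-approximation (Wald) form. The printed half-widths do not agree with those inputs, and both err towards greater precision.

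Little is at stake, but something is. The section says that 20 participants may give adequate precision for planning a future study, and these two intervals are the only numerical precision statement it offers. A reader who recomputes them will not recover them, and the text does not show how they were obtained.

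**Working it through.** **Inputs.** From section 11.2: n = 20 subjects, 95% confidence, observed proportions 0.50 and 0.80, stated half-widths 0.20 and 0.16. Each subject receives both drinks and contributes one yes/no comparison, so the denominator is the number of subjects. The method is not named. The Wald form is assumed first because the intervals are printed as symmetric about the estimate.

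**Step 1: try to reproduce the stated figures at n = 20.** Half-width = 1.96 × √(p(1−p)/n).

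- p = 0.50: 1.96 × √(0.25/20) = 1.96 × 0.1118 = 0.219, so 28.1% to 71.9%. Stated: 30% to 70%.
- p = 0.80: 1.96 × √(0.16/20) = 1.96 × 0.0894 = 0.175, so 62.5% to 97.5%. Stated: 64% to 96%.

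Neither is reproduced, and rounding to whole points does not close the gap.

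**Step 2: find the n that the stated figures imply.** n = 1.96² × p(1−p)/h².

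- p = 0.50, h = 0.20: 3.8416 × 0.25/0.04 = 24.0
- p = 0.80, h = 0.16: 3.8416 × 0.16/0.0256 = 24.0

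If the half-widths were rounded to whole points, the first is compatible with n from 22.9 to 25.3 and the second with 22.6 to 25.6. In whole subjects that is 23 to 25, which excludes 20. The two figures also stand in the Wald ratio: 16/20 = 0.80 = √(0.16/0.25). They agree with each other but not with the stated sample.

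**Step 3: try other methods at n = 20** (10/20 and 16/20 observed; all 95%).

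| Method | At 50% | At 80% | Half-widths (points) |
|---|---|---|---|
| Stated | 30% to 70% | 64% to 96% | 20 / 16 |
| Wald, 1.96 | 28.1% to 71.9% | 62.5% to 97.5% | 21.9 / 17.5 |
| Wald, multiplier 2 | – | – | 22.4 / 17.9 |
| Wald, t with 19 df | – | – | 23.4 / 18.7 |
| Wald, continuity-corrected | – | – | 24.4 / 20.0 |
| Wilson | 29.9% to 70.1% | 58.4% to 91.9% | 20.1 / 16.8 |
| Agresti–Coull | 29.9% to 70.1% | 57.8% to 92.5% | 20.1 / 17.3 |
| Plus-four | – | – | 20.0 / 17.3 |
| Jeffreys | 29.3% to 70.7% | 59.2% to 92.9% | 20.7 / 16.8 |
| Mid-P | 28.9% to 71.1% | 58.5% to 93.3% | 21.1 / 17.4 |
| Clopper–Pearson | 27.2% to 72.8% | 56.3% to 94.3% | 22.8 / 19.0 |

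None gives the stated pair. Wilson, Agresti–Coull and plus-four reach about ±20 at 50%. At 80% their intervals are wider than ±16 and are not centred on 80%, so they could not be written as 80% plus or minus a half-width.

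**Step 4: check the confidence level.** At n = 20 the stated half-widths equal 0.20/0.1118 = 0.16/0.0894 = 1.79 standard errors, which is about 92.6% Wald confidence. A 90% Wald interval would give 18.4 and 14.7 points, so a switch to 90% does not explain them either.

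**Step 5: check whether the power statement is affected.** A two-sided paired t-test with n = 20, dz = 0.66 and α = 0.05 has power 79.9%, which agrees with the β = 0.2 in section 11.1. That calculation is separate and stands.

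**The case against.** The strongest reply is that section 11.2 names no method, so a shortfall of 1.9 and 1.5 points holds only under the Wald reading. Compared on width alone, other methods at n = 20 come closer: Wilson has half-widths of 20.1 and 16.8, and highest-density Bayesian intervals have 20.2 and 16.5 (uniform prior) or 20.7 and 16.4 (Jeffreys prior). The ±20% figure taken alone could be a rounded Wilson or Agresti–Coull interval. This stands in part. The ±16% figure is the firmer evidence, and the size of the error depends on the method. It does not rescue the text, because none of these intervals is centred on 80% and none rounds to the pair 20 and 16.

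A second reply is that putting n + 4 = 24 in the denominator while keeping the unadjusted proportion gives 20.0 and 16.0 points. That is not a standard interval and the documents do not mention it. It does show that the implied 24 should not be read as evidence of a different planned sample size. The origin of the figures cannot be determined.

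A third reply is that nothing depends on these intervals. The section calls the assessment rough and indirect, the study is a pilot, the proportion is not an outcome in section 11.1, and no decision rule uses it. This stands, and it is why the point ranks low. But roughness describes the use of a proportion as a stand-in for other parameters. It does not change what a 95% interval for 20 subjects is.

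**Conclusion.** The concern holds as a minor arithmetic error. Under the symmetric 95% formula, which the notation implies but the section does not name, the half-widths for 20 subjects are 21.9 and 17.5 points, not 20 and 16. The stated values are too small by 1.9 and 1.5 points, about 9% in relative terms (20/21.9 and 16/17.5 are both about 0.91). The lower limits should be 28.1% and 62.5%, not 30% and 64%. No other method tried at n = 20 yields both stated intervals. Enrolment, the primary mixed-model analysis and the power statement are unaffected. Confidence in the arithmetic is high.

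**What to change.** In section 11.2, replace the two half-widths with the n = 20 values, 50% ± 21.9% and 80% ± 17.5%, and say that they are normal-approximation intervals. Alternatively, name another method and print its limits for 20 subjects: for example Wilson, 30% to 70% and 58% to 92%, or exact (Clopper–Pearson), 27% to 73% and 56% to 94%. If a different n or an adjustment was intended, state it. The cost is two figures in one paragraph, with no change to enrolment, analysis or the power statement.

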11.3 DATA MANAGEMENT

The glucose solution will be acquired from Azer Scientific and stored in a secure air-conditioned facility. The solution will be packaged and shipped in shatter-proof 10 fluid ounce plastic bottles with clear labels

Data will be stored in a password-protected cloud-based data system that does not contain any participant information. Individual records are referred to by dummy identifiers that cannot be traced back to the study participants except with the master code list that is stored separately in a secured location.

12 DATA HANDLING AND RECORD KEEPING

The study coordinator and research assistants are responsible for the accuracy, completeness, legibility, and timeliness of the data reported.

12.1 PHI AND HIPAA

Information about study participants will be kept confidential and managed according to the requirements of the Health Insurance Portability and Accountability Act of 1996 (HIPAA). Those regulations require a signed subject authorization informing the subject of the following:

- What protected health information (PHI) will be collected from the participants in this study
- Who will have access to that information and why
- Who will use or disclose that information
- The rights of a research subject to revoke their authorization for use of their PHI.

In the event that a participant revokes authorization to collect or use PHI, the investigator, by regulation, retains the ability to use all information collected prior to the revocation of participant authorization. For participants that have revoked authorization to collect or use PHI, attempts should be made to obtain permission to collect at least vital status (i.e., that the subject is alive) at the end of their scheduled study period.

